### 5.4.3 Other Efficacy Analyses

All the efficacy exploratory analyses will be performed in both evaluable analysis set and/or full analysis set.

The observed clinical benefit rate and the disease control rate will be presented along with their 95% CI of exact method.

Similarly, using the same method as the analyses to PFS and OS, the Duration of Response (DOR) will be analyzed using Kaplan-Meier method and the estimated median, first and third quartiles of the DOR will be presented with the 95% CI.

## 5.5 Pharmacokinetic, Pharmacodynamic, Pharmacogenomic, and Other Biomarker Analyses

Not applicable.

## 5.6 Safety Analyses

All safety analyses will be performed based on Full Analysis Set.

### 5.6.1 Extent of Exposure

The analyses of extent of drug exposure will be performed for each subject on the duration of treatment, and total cumulative dose received (mg) (i.e., the sum of all doses actually taken), actual dose intensity (mg/day) received, and the relative dose intensity (%), and the definitions are:

- Duration of treatment (day) is calculated as (Date of last study drug – Date of first study drug + 1)
- Actual dose intensity (mg/day) is calculated as total cumulative dose received (mg) divided by treatment duration (day)
- Relative dose intensity (%) is calculated as actual dose intensity (mg/day) divided by 24 (mg/day).

For the data from the CRF page of Study Medication collected during treatment phase, the number (%) of subjects with dose reduced, dose interruption, and the time to the first dose reduction will be summarized.

### 5.6.2 Adverse Events

The adverse event (AE) verbatim descriptions (investigator terms from the CRF) will be classified into standardized medical terminology using the Medical Dictionary for Regulatory Activities (MedDRA). Adverse events will be coded to the MedDRA (Version 21.0 or higher) lower level term (LLT) closest to the verbatim term. The linked MedDRA preferred term (PT) and primary system organ class (SOC) will also be captured in the database. All AEs will also be graded by the investigators using CTCAE v4.03.

A treatment-emergent adverse event (TEAE) is defined as an AE that emerged during treatment (up to 28 days post the last study dose), having been absent at pretreatment (Baseline) or

- Reemerged during treatment (up to 28 days post the last study dose), having been present at pretreatment (Baseline) but stopped before treatment, or
- Worsened in severity during treatment (up to 28 days post the last study dose) relative to the pretreatment state, when the AE was continuous.

Only those AEs that are treatment emergent will be included in summary tables. All AEs, treatment emergent or otherwise, will be presented in subject data listings.

The incidence of TEAEs will be reported as the number (percentage) of subjects with TEAEs by SOC and PT. A subject will be counted only once within a SOC and PT, even if the subject experienced more than 1 TEAE within a specific SOC and PT. The number (percentage) of subjects with TEAEs will also be summarized by highest CTCAE grade.

The number (percentage) of subjects with treatment-related TEAEs will also be summarized by SOC and PT. Treatment-related TEAEs include those events considered by the investigator to be related to study treatment or with missing assessment of the causal relationship.

The following TEAE summary analyses will be performed:

- An overall summary table will include the number (%) of subjects with TEAEs, with treatment-related TEAEs, with TEAEs with CTCAE grade  $\geq 3$ , with severe TEAEs (grade 3 or 4), with serious TEAEs, treatment-related serious TEAEs, TEAEs leading to death, TEAEs leading to dose withdrawn/dose reduced/dose interrupted.
- TEAEs will be summarized by SOC, PT and grade in number (%) of patients. Similarly, TEAEs that are serious, treatment-related, grade 3 or above, serious and related, leading to death/dose withdrawn/dose reduced/dose interrupted will also be summarized by SOC, PT and grade.
- TEAEs will be summarized by PT in number (%) of subjects.
- Additional summary on the TEAE of special interest will be presented by special interest, preferred term, and the worst CTCAE grade.

#### 5.6.2.1 Deaths

An overall summary of deaths will be presented: deaths within 28 days post last study drug, and deaths after 28 days post last study drug, and treatment-related deaths. A listing of all deaths will be provided.

#### 5.6.3 Laboratory Values

Per protocol, the clinical laboratory tests in [Table 1](#) were performed in the study. Abnormal laboratory values will be flagged and identified as those outside (above or below) the normal range, laboratory values will also be categorized by CTCAE v4.03 grades per Appendix 7, Sponsor's Grading for Laboratory Values, of the study protocol. Laboratory values will be summarized by visit and by worst post-baseline visit. Laboratory parameters will be summarized by worst grade, and laboratory parameters with CTCAE grading in both high and low directions will be summarized separately. Shift tables from baseline grade to worst value will be presented.

**Table 1 Clinical Laboratory Tests**

Category	Parameters
Hematology	Hematocrit, hemoglobin, platelets, RBC count, and WBC count with differential (bands, basophils, eosinophils, lymphocytes, monocytes, neutrophils), ANC, INR b
Chemistry	
Electrolytes	Bicarbonate, chloride, magnesium, potassium, sodium
Liver function tests	Alanine aminotransferase, alkaline phosphatase, aspartate aminotransferase, direct bilirubin, total bilirubin
Renal function tests	Blood urea/blood urea nitrogen, creatinine
Thyroid function tests a	TSH and free T4
Pregnancy test	Serum $\beta$ -hCG (if urine not tested)
Other	Albumin, glucose c , lactate dehydrogenase, total protein, uric acid, calcium, phosphorus
Urinalysis	Glucose c , ketones, pH, protein, RBCs, specific gravity
Pregnancy test	Urine $\beta$ -hCG (if serum not tested)

ALT = alanine aminotransferase, ANC= absolute neutrophil count, AST = aspartate aminotransferase,  $\beta$  hCG = beta-human chorionic gonadotropin, INR = International Normalized Ratio, RBC = red blood cells, T4 = thyroxine, TSH = thyroid stimulating hormone, WBC = white blood cells

a: Thyroid function will be assessed at the Screening Visit and then every 2 cycles (starting at C2) throughout the study.

b: INR only at screening/baseline and when clinically indicated

c: Fasting glucose at Screen, only

#### 5.6.4 Vital Signs

Descriptive statistics for vital signs parameters (diastolic and systolic blood pressure, pulse, respiration rate, temperature, weight) and changes from baseline will be presented by visit.

#### 5.6.5 Electrocardiograms

Descriptive statistics for ECG parameters and changes from baseline will be presented by visit.

Shift tables will present changes from baseline in ECG (categorized as normal; abnormal, not clinically significant; and abnormal, clinically significant) to the worst post-baseline (during treatment period). Other ECG values (Heart rate, QT Interval) and the changes from baseline will be summarized and presented by visit.

#### 5.6.6 Other Safety Analyses

No other safety analyses are planned.

## 5.7 Other Analyses

No other analysis is planned.

## 5.8 Exploratory Analyses

Additional exploratory analyses may be conducted as appropriate. Any exploratory analyses to be performed will be appropriately titled/labeled as exploratory and will be clearly distinguished from planned analyses when results are reported in the Clinical Study Report.

## 6 INTERIM ANALYSES

Per study protocol, one interim analysis was planned to be performed after the first 20 evaluable subjects complete at least 2 tumor assessments or discontinue treatment due to any reason. From the interim analysis the enrollment would be halted if the number of responders is 3 or less ( $ORR \leq 15\%$ ), and the safety and efficacy data would be further evaluated before making the decision of stopping the study permanently.

The study team would define the datasets for the interim analysis. The study team would assess the impact of any issues such as unsolved data queries, missing data or data entry delays on the interim results. The study statistician would perform the interim analysis, which would include calculating ORR per protocol.

## 7 CHANGES IN THE PLANNED ANALYSES

Treatment duration will be analyzed in months instead of nominal cycles mentioned in the protocol. The exploratory analyses of identifying and exploring tumor and blood biomarkers that correlate with clinical outcomes, including efficacy will not be performed.

## 8 DEFINITIONS AND CONVENTIONS FOR DATA HANDLING

Baseline: in all analyses, the baseline value is defined as the non-missing value most recently collected before the first dose.

Study day calculation: unless otherwise specified in outputs, the following convention will be used to calculate the study day used in the listings:

- Day 1 is the day of the first study drug taken
- Study Day (for an event/assessment, relative to the day of the first study drug taken) is defined as (date of assessment/event – date of the first study drug taken +1) for the event/assessment on or after the date of the first study drug, and as (date of assessment/event date of the first study drug) for the event/assessment before the first study drug.

Censoring rule for OS: Subjects who were lost to follow-up, or withdrew consent, will be censored at the last date the subject was known to be alive, otherwise the censoring date will be the data cutoff date.

Censoring rule for PFS: [Table 2](#) shows the censoring rules for subjects without documented PD or death in the derivation of PFS based upon investigator's tumor assessment.

Censoring rule for duration of response (DOR): considering the subjects with the confirmed best overall response of CR or PR and still alive without disease progression following the objective response. The same censoring rule of PFS will be applied to the derivation of DOR for the cases applicable.

**Table 2 Censoring Rules for Analysis of Progression-Free Survival**

No.	Situation	Date of Progression or Censoring	Outcome
1	No baseline tumor assessments	Date of first dose	Censored
2	Progression documented between scheduled visits	Date of first radiological PD assessment	Progressed
3	No progression at the time of data cut-off or withdrawal from study	Date of last adequate radiologic assessment prior to or on date of data cut-off or withdrawal from study, or date of the first dose if no adequate post baseline tumor assessment was conducted.	Censored
4	New anticancer treatment started	Date of last adequate radiologic assessment prior to or on date of new anticancer treatment, or date of the first dose if no adequate post baseline tumor assessment was conducted.	Censored
5	Death before first PD assessment	Date of death	Progressed
6	Death between adequate assessment visits*	Date of death	Progressed
7	Death or progression after two or more missed visits**	Date of last adequate radiologic assessment before missed tumor assessments, or date of the first dose if no adequate post baseline tumor assessment was conducted.	Censored
8	No post-baseline tumor assessments but known alive	Date of first dose	Censored

CR = complete response, PD = progressive disease, PR = partial response, SD = stable disease,

\* Adequate tumor assessment is a radiologic assessment of CR, PR, SD, non-CR/non-PD or PD as determined by investigators.

New anticancer treatment includes palliative radiotherapy. Any tumor assessments after new anticancer treatment started will be removed in the definition of PFS.

\*\* 'More than two missed visits' occurs if the duration between the last tumor assessment and death or PD is longer than the following:

[figure not shown]
1. 12 weeks if the last tumor assessment is prior to week 24
2. 16 weeks if the last tumor assessment is on or after week 24

Note: NE counts as a non-missing visit for No. 7.

Censoring rules are also described in [Figure 1](#).

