9.5.1.3.1 TUMOR ASSESSMENTS

Tumor assessments will be performed using RECIST 1.1. Assessments are to be performed at the site by appropriately qualified personnel at each time point and results of the site interpretation are to be recorded on the appropriate CRFs. Historical standard of care scans that are performed with scanning parameters consistent with the requirements for this protocol within 21 days prior to dosing are acceptable. Tumor assessments (CT chest and CT/MRI of neck, abdomen, pelvis, and other areas of known disease at screening plus any areas of newly suspected disease) should be performed at screening, every 6 weeks \pm 1 week

for the first 24 weeks and every 8 weeks \pm 1 week thereafter, or sooner if clinically indicated, until documentation of disease progression. A bone scan and brain scan will be performed within 21 days prior to C1D1, and continuing from C1D1 every 24 weeks \pm 1 week, or as clinically indicated. If PET/CT is performed, a bone scan is not necessary. In addition, for subjects with a history of treated brain metastases, brain scans will be performed at tumor assessment time points, if clinically indicated. In subjects with CR based on body CT/MRI scans, a bone scan (or PET/CT, if performed at Screening) and brain scan assessment will be required at response confirmation. All objective responses must be confirmed at least 28 days following the initial achievement of the response.

The CT scan should be a diagnostic quality spiral or multidetector CT with oral and iodinated IV contrast, and the MRI scan should be performed with IV gadolinium chelate. Scans of the neck, abdomen, pelvis, and other areas of the body may be done with MRI instead of CT, but evaluation of the chest must be done with CT. If iodinated IV contrast is contraindicated, the chest evaluation should be done with non-contrast CT, and the abdomen and pelvis evaluation should be performed using either CT with oral contrast (without IV contrast) or MRI with gadolinium chelate IV contrast (the latter is preferred). Spiral/multidetector CT should be performed with a 5-mm contiguous slice reconstruction algorithm. If body MRI scans are performed, contiguous slices of 5 mm are also recommended.

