 - u. Tumor assessments will be performed using RECIST 1.1. Screening tumor assessments using contrast-enhanced CT of the chest and contrast-enhanced CT or MRI of the neck/abdomen/pelvis and other areas of known disease or newly suspected disease should be performed within 21 days prior to C1D1. Treatment Phase: tumor assessments of the chest/neck/abdomen/pelvis and other areas of known disease at screening or newly suspected disease should be performed every 6 weeks (± 1 week) for the first 24 weeks and every 8 weeks ± 1 week thereafter, or sooner if clinically indicated, until documentation of disease progression and should utilize the same methodology and scan acquisition techniques used at screening to ensure comparability. If a subject discontinues from the study prior to the Week 6 scan, then a CT/MRI scan should be performed as close as possible to 6 weeks after C1D1 but before another anticancer therapy is initiated. Detailed image acquisition guidelines will be provided by the imaging core laboratory.

Follow-up Period: Subjects who discontinue treatment without disease progression should continue tumor assessments every 6 weeks (± 1 week) for the first 24 weeks and every 8 weeks ± 1 week thereafter, until disease progression or beginning another anticancer therapy.
 - v. A brain scan and bone scan (99m Tc-tetraphosphonate scintigraphy, whole body bone MRI, or 18 F-NaF) to assess brain and bone metastases will be performed within 3 weeks prior to C1D1 (historical scans are acceptable) and then every 24 weeks (± 1 week), or sooner if clinically indicated. If PET/CT is performed, a bone scan is not necessary. For subjects with a history of treated brain metastases, brain scans will be performed at tumor assessment time points, if clinically indicated. In subjects with CR based on body CT/MRI scans, a bone scan (or PET/CT, if performed at Screening) and brain scan assessment will be required at response confirmation. All objective responses must be confirmed at least 28 days following the initial achievement of the response. The same methodology and acquisition techniques used at screening should be used throughout the study to ensure comparability. Lesions identified on bone scans should be followed with cross-sectional imaging.
 - w. Concomitant medications will be recorded throughout and for 28 days after last dose of lenvatinib. All anticancer therapy will be recorded until time of death or termination of survival follow-up.

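### PFS censoring rows 5 and 7 overlap for deaths without a post-baseline scan, and the 12-week clock can start at the screening scan, before the first dose

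*SAP*

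**What the plan says.** The rules are in SAP Section 8, Table 2.

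- **Row 5**, "Death before first PD assessment": an event on the date of death.
- **Row 7**, "Death or progression after two or more missed visits": censored. The date is given as "Date of last adequate radiologic assessment before missed tumor assessments, or date of the first dose", the latter where there was no adequate assessment after baseline.
- **Footnote to row 7**: the condition "occurs if the duration between the last tumor assessment and death or PD is longer than the following", namely "12 weeks if the last tumor assessment is prior to week 24", and 16 weeks from week 24 on. The footnote introduces this as the case of more than two missed visits, while the row heading says two or more.
- **Row 8**: a subject with no post-baseline assessment is censored at first dose, but only if known to be alive.

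The protocol treats screening imaging as a tumor assessment. Section 9.5.1.3.1 lists the scans, "plus any areas of newly suspected disease) should be performed at screening", and Table 4 footnote u speaks of "Screening tumor assessments using contrast-enhanced CT of the chest", to be done within 21 days before C1D1. SAP 5.1.2 reads 12-week PFS from the Kaplan-Meier curve at day 84. Protocol 9.7.1.6.2 counts death as a PFS event and claims superiority if the lower 95% limit is above 50%.

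**The concern.** A subject who stops early, has no post-baseline scan, starts no new anticancer therapy and later dies can fall under two rows with opposite outcomes. Row 5 puts an event at the death. Row 7 takes the subject out of the risk set at first dose, as if nothing had been observed. Two programmers could code the same death differently, and in an open-label trial the choice could be made after outcomes are known.

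The footnote makes this relevant to the landmark. Its clock is not limited to post-baseline assessments, so for a never-scanned subject it runs from a scan taken before treatment began. A known death before day 84 can then be censored after a single missed scan. The endpoint is compared with a fixed 50% limit, and the protocol (Section 7.1.1) describes a disease with median survival of 3 to 5 months, so deaths in this period are to be expected.

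**Working it through.** **1. The plan's own figure.** Inputs from SAP Section 4 and Protocol 9.7.1.6.2: n = 57, exponential PFS with 70% at 12 weeks, about 45 events on average, Greenwood 95% CI, success if the lower limit exceeds 50%. In 5,000 runs with plain Greenwood limits, power is 0.863 (exponential censoring), 0.875 (uniform) and 0.890 (18-month accrual with administrative censoring). The stated 0.877 is reproduced. It is not in dispute, and the plain limits are used below.

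**2. When row 7 starts to apply.** SAP Section 8 has no Day 0: Day 1 is the first dose, and Day -s is s days before it. A death on study Day d is s + (d - 1) days after a scan on Day -s. Row 7 needs s + d - 1 > 84, that is d ≥ 86 - s.

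| Start of clock | First study day on which row 7 applies |
|---|---|
| Scan on Day -21 | 65 |
| Scan on Day -14 | 72 |
| Scan on Day -7 | 79 |
| Scan on Day -2 | 84 |
| First dose (Day 1) | 86 |

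Example: scan on Day -21, death on Day 75. The gap is 21 + 74 = 95 days. Row 5 gives an event on Day 75; row 7 gives censoring at first dose.

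**3. Heading against footnote.** Scans are due at weeks 6 and 12, each ±1 week. On Days 65-84 the week-6 window has closed and the week-12 window (week 11 to week 13) has not. One visit has been missed, so the row heading is not met although the footnote's duration is.

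**4. Effect near the limit (n = 57, no other censoring).** Lower limit = p - 1.96 × √[p(1 - p)/n].

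- 35/57: p = 0.614, SE = 0.0645, lower limit 48.8%; not above 50%.
- Two of the 22 failures are unscanned deaths on Days 65-84 and are moved to first-dose censoring. 35/55: p = 0.636, SE = 0.0649, lower limit 50.9%; above 50%.
- 36/57: lower limit 50.6%, so the claim is met without any censoring.

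**5. How many deaths are exposed.** With a Day -21 scan and the SAP's exponential model, all PFS events on Days 65-84 number 57 × (0.70^(64/84) - 0.70) = 3.5 at 12-week PFS of 70%, and 57 × (0.50^(64/84) - 0.50) = 5.1 at 50%. These are ceilings, because only deaths with no post-baseline scan count. The documents give no unscanned share. Assuming 5-20%:

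- low end: 57 × 0.05 × 0.062 = 0.2 deaths;
- high end, with all unscanned subjects dead by Day 84 and deaths spread evenly: 57 × 0.20 × 20/84 = 2.7.

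If every scan were on Day -7, the exposed window would be Days 79-84 and the high end 57 × 0.20 × 6/84 = 0.8.

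**6. Direction.** Row 7 also drops unscanned deaths after day 84, which row 5 would keep as event-free at 12 weeks. Assume 10% unscanned, Day -21 scans, 70% 12-week PFS among the scanned, and unscanned subjects followed until death.

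- All unscanned subjects die by Day 84, evenly spread. Row 5: 0.9 × 0.70 = 63.0%. Row 7: 0.63/(0.9 + 0.1 × 64/84) = 64.5%.
- Unscanned subjects have the same 70% survival at Day 84. Row 5: 0.63 + 0.07 = 70.0%. Row 7: 0.63/(0.9 + 0.1 × 0.238) = 68.2%, where 0.238 = 1 - 0.70^(64/84).

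**The case against.** - **Figure 1 may settle the order.** The SAP says the chart also describes the rules, and it cannot be seen here. This stands: a reader might infer that the plan has no precedence at all, and the documents do not support going that far. What can be said is that Table 2's readable text sets none and must be reconciled with the chart.
- **Row 7 may be a deliberate exception.** Any death without PD precedes a first PD assessment, so if row 5 always won, row 7's death clause would be empty. That is fair. But letting row 5 win only where no post-baseline scan exists leaves row 7 in force for scanned subjects. Its first-dose fallback still serves late progressions and subjects whose only scans were not evaluable.
- **The clock could start at first dose.** Then row 7 first applies on Day 86 and removes no death by Day 84. This also stands. The footnote does not say so, however, and its literal wording points to the screening scan.
- **Few subjects are exposed.** Footnote u asks for a scan near week 6 even after early discontinuation, and Days 65-84 is the window only for a Day -21 scan. Both are right.

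Two stronger readings are tempting. One is that the fastest-declining patients are lost from the analysis; in fact, with a scan inside the 21-day window, an unscanned death before Day 65 falls under row 5 alone and is an event. The other is that row 7 always flatters 12-week PFS; step 6 of the working shows it can go either way.

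**Conclusion.** The point holds as an overlap between two rules, with an unsuitable start date for the clock. A never-scanned subject who dies more than 12 weeks after the last tumor assessment satisfies both rows. The literal clock can bring this forward to study Day 65, against row 7's own heading. A subject with any post-baseline scan cannot lose a death before day 84 in this way.

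The size is modest: about 0.2 to 2.7 deaths of 57 if 5-20% of subjects are unscanned and every screening scan is on Day -21, and fewer with later scans. Both inputs are assumptions. The move from 48.8% to 50.9% is a boundary illustration at the planned n = 57, not a forecast. SAP 5.4.2 runs the secondary analyses in the FAS, whose size is not fixed, and restates no 50% rule; that rule is in Protocol 9.7.1.6.2. The correction is still worth making, because a known death can be censored at first dose after one missed scan on an endpoint judged against a fixed limit.

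**What to change.** In SAP Table 2 and its footnote, and in Figure 1 where it differs:

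1. Where no post-baseline scan exists, start the row 7 clock at first dose and never at the screening scan.
2. State which of rows 5 and 7 prevails for such a subject. Row 5 agrees with the protocol's PFS definition and with row 8, which limits first-dose censoring of unscanned subjects to those known to be alive. This is needed even with the new clock, because deaths from Day 86 on still meet both rows.
3. Use one definition of missed visits in the row heading and the footnote.
4. Add one sensitivity analysis of 12-week PFS in which every death without earlier PD or new anticancer therapy is an event, whatever scans were missed.

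The cost is a few sentences and one extra Kaplan-Meier run. The estimate may come out slightly less favourable.

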#### 5.1.1 Primary Endpoint

The primary efficacy endpoint is ORR as determined by investigator review, using RECIST 1.1. ORR is the proportion of subjects who have best overall response (BOR) of CR or PR (confirmed). Confirmation of CR or PR must be performed at least 28 days following the initial achievement of the response.

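### The SAP's gap test for missed scans allows nothing for visit windows and mishandles gaps that cross week 24, so PD after one missed scan can be censored

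*SAP*

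**What the plan says.** SAP Section 8, Table 2, row 7 covers "Death or progression after two or more missed visits" and moves the subject to a censoring date at the last adequate scan before the gap, or at first dose if there is none. The footnote to that row names the situation differently, as "More than two missed visits", and replaces the count by elapsed time. The situation "occurs if the duration between the last tumor assessment and death or PD is longer than the following":

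- "12 weeks if the last tumor assessment is prior to week 24"
- "16 weeks if the last tumor assessment is on or after week 24"

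A note adds that "NE counts as a non-missing visit for No. 7". Row 6 of the same table counts a death between adequate assessment visits as an event. For duration of response, Section 8 states: "The same censoring rule of PFS will be applied to the derivation of DOR".

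The scan schedule is in Protocol 9.5.1.3.1 and Table 4: every 6 weeks ±1 week for the first 24 weeks, then every 8 weeks ±1 week. Nominal visits are therefore weeks 6, 12, 18, 24, 32, 40, 48 and so on. Off-schedule scans can also occur, because earlier scans are allowed if clinically indicated and "Confirmation of CR or PR must be performed at least 28 days following the initial achievement of the response" (SAP 5.1.1).

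**The concern.** Row 7 names a number of missed visits, but the footnote tests a number of weeks. The two agree only if the limits separate one missed scan from two on this trial's schedule. Limits of exactly two nominal intervals do not: a subject who misses one scan and attends the next a few days late has a gap just over the limit. A subject whose missed scan is the one at week 24 has a longer nominal gap than the 12-week limit foresees, because the interval changes there.

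When the test misfires, an observed progression is discarded and the subject is censored at an earlier scan. The rule feeds 12-week and median PFS (secondary) and DOR (exploratory), in a single-arm trial that is read against historical control. Which events count would depend on a few days of scheduling, or on how a programmer reads week 24.

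**Working it through.** **Inputs.** Schedule and ±7-day windows from Protocol Table 4; limits of 84 and 112 days from SAP Table 2. The limits reproduce as 2 × 6 = 12 weeks and 2 × 8 = 16 weeks, with nothing added for windows.

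**Progression after exactly one missed scan.** Let a and b be the day offsets of the last scan and of the scan showing PD, each from −7 to +7. That gives 15 × 15 = 225 day pairs. The gap is the nominal gap + (b − a).

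- *Weeks 6 to 18 and 12 to 24:* nominal gap 84 days, limit 84. Censored if b > a: (225 − 15)/2 = 105 pairs, and 105/225 = 46.7%. Weeks 32 to 48 (112 days against 112) give the same share.
- *Weeks 18 to 32, week 24 missed:* nominal gap 98 days, limit 84. Censored unless b − a = −14, which is one pair: 224/225 = 99.6%. At exact scheduled dates, 14 weeks exceeds 12, so windows play no part.
- *Weeks 24 to 40:* nominal gap 112 days. If the nominal visit sets the limit (112), 105/225 = 46.7%. If the actual date sets it, a scan done on one of the 7 days before week 24 gets the 84-day limit. All 7 × 15 = 105 such pairs are censored (smallest gap 106 days). The other 8 days give 7 + 6 + … + 0 = 28 pairs. Total 133/225 = 59.1%.

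**Separation of one miss from two.**

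| Last scan | No miss, largest gap | One miss, largest gap | Two misses, smallest gap | SAP limit |
|---|---|---|---|---|
| Week 6 | 8 weeks | 14 weeks | 16 weeks | 12 weeks |
| Week 12 | 8 weeks | 14 weeks | 18 weeks | 12 weeks |
| Week 18 | 8 weeks | 16 weeks | 20 weeks | 12 weeks |
| Week 24 or later | 10 weeks | 18 weeks | 22 weeks | 16 weeks (12 if the week-24 scan is early and actual dates apply) |

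PD with no missed scan is never censored, and PD after two missed scans always is. On the scheduled grid the errors for PD fall only on one-miss cases and only as over-censoring. Because PD after exactly two misses is always censored, the test is also at odds with the footnote's own label.

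**Deaths.** With the last scan on day 126 (week 18), the limit is reached on day 126 + 84 = 210 (week 30). The scan after week 24 is due on day 224 (week 32). A death between those dates follows one missed visit and is censored if row 7 prevails over row 6.

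**Direction for 12-week PFS.** A discarded PD lies more than 84 days after the last scan. If the gap starts at a post-baseline scan, or at first dose when there is none, that PD is later than week 12. The subject was event-free at week 12 under a visit count. Censoring such a subject earlier can only leave the 12-week Kaplan-Meier estimate unchanged or lower it.

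**Size, by simulation under assumptions.** The documents give no miss rate. Assumed: 5%, 10% or 20% of scans missed independently, n = 57, exponential PFS, PD only, cut-off uniform over 6 to 24 months, scan dates uniform in their windows. The SAP test is compared with a count of closed windows.

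| True 12-week PFS 70% | 5% missed | 10% missed | 20% missed |
|---|---|---|---|
| PD events over-censored per trial | 2.1 | 3.7 | 6.0 |
| Mean rise in median PFS (months) | 0.12 | 0.27 | 0.62 |
| Rise in the typical (median) run (months) | 0 | 0.03 | 0.13 |

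The standard deviation of the estimated median is 1.1 to 1.25 months. At a true 12-week PFS of 50%, the mean rise is at most 0.10 months and the typical run does not move. Across the scenarios run, the 12-week estimate falls by 0.2 to 0.8 points (true 70%) or 0.5 to 2.4 points (true 50%).

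**The case against.** The best defence is that the footnote is the definition. An elapsed-time test is prespecified and reproducible, and *more than two* is a slip because the limits decide the outcome. It is true that the test can be programmed apart from the reading of week 24. But row 7 states what the test is for, and the test does not deliver it.

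Four stronger readings are tempting, and the documents do not support them.

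- *The limits ignore the change of interval.* They do not: they move from 12 to 16 weeks at week 24. The fault is that the switch follows the last scan, so gaps crossing week 24 are misjudged. On exact dates away from that crossing, the strict inequality protects PD after one miss.
- *Deaths are misclassified at known rates.* Row 6 counts a death between adequate visits as an event, the visible text does not rank rows 6 and 7, and Figure 1 is not shown. Any general death percentage would also depend on when a scan is deemed missed, so none is claimed.
- *The error runs in both directions.* An off-schedule case can be built: extra scan on day 56, weeks 12 and 18 missed, death on day 137. The gap is only 81 days, so the death counts. With early and confirmatory scans added to the simulation, such under-censoring stayed below 0.01 events per trial.
- *The rule flatters the efficacy claim.* ORR does not use it, and 12-week PFS, the only PFS measure tested against a threshold (Protocol 9.7.1.6.2), moves down if at all. One caveat: if a programmer measured the gap from a screening scan up to 21 days before first dose, that direction would not be assured for subjects with no post-baseline scan.

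It also stands that the percentages are conditional on a missed scan, and that the effect on estimates is small.

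**Conclusion.** The concern holds in a limited form. As written, the footnote can censor PD after exactly one missed scan although every attended scan is in window. The shares above treat all in-window day pairs as equally likely; the week 18 to 32 case needs no such assumption. Row 7 and its footnote also disagree on the count, and week 24 can be read as the nominal visit or the actual date. The net effect is a slight tendency to lengthen median PFS and DOR, by an amount that rests on miss rates the documents do not give. Nothing here threatens the primary analysis. Severity: minor, but worth correcting before database lock. Since Figure 1 could not be seen, it may already settle some of these points.

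**What to change.** In SAP Table 2:

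1. Use *two or more* in both row 7 and the footnote.
2. Replace the 12- and 16-week test by a count of scheduled assessments (weeks 6, 12, 18, 24, then 8-weekly, each ±1 week, or the schedule that applies off treatment) whose window closed without a scan before the event.
3. Assign every off-schedule scan, whether early, confirmatory or late, to the nearest scheduled visit by a fixed rule, with ties specified.
4. Keep NE as non-missing.
5. State whether row 6 or row 7 prevails for deaths, and align Figure 1 with the text.

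If an elapsed-time test is preferred, limits set by the nominal visit of the last scan give the same result for PD on the scheduled grid: over 14 weeks (last scan at week 6 or 12), over 16 weeks (week 18) and over 18 weeks (week 24 or later). These follow from the separation table above and lose none of the intended censoring after two missed scans.

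The cost is SAP wording and programming only. Visit windows must be derived for each subject, and median PFS and DOR may come out slightly shorter.
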